6.3. Definition of Dose Limiting Toxicity (DLT)

A DLT is defined as any of the following study drug-related toxicities (defined as at least possibly related to study drug) **occurring in the first cycle** of study treatment:

Hematological:

- \geq Grade 4 neutropenia lasting > 7 days;
- Febrile neutropenia;
- Any Grade 3 thrombocytopenia with bleeding or a requirement for platelet transfusions;
- \geq Grade 4 thrombocytopenia (platelets $< 25,000/\mu\text{L}$).

Non-hematological:

- AST or ALT $> 3 \times$ ULN and concurrent total bilirubin $> 2 \times$ ULN without initial findings of cholestasis (e.g. findings consistent with Hy's law or FDA definition of potential drug-induced liver injury [pDILI]);
- \geq Grade 4 AST or ALT of any duration;
- Any \geq Grade 3 non-hematologic toxicity with the following exceptions:
 - Grade 3 immune-related AE (irAE) that resolves to \leq Grade 1 or to baseline with immunosuppressive therapy within 3 weeks;
 - Grade 3 fatigue that persists < 7 days;
 - Grade 3 rash that resolves to \leq Grade 1 within 3 weeks;
 - Grade 3 or 4 elevation in serum amylase and/or lipase that are not associated with clinical or radiographic evidence of pancreatitis;

- \geq Grade 3 electrolyte abnormality that lasts $<$ 72 hours, is not clinically complicated, and resolves spontaneously or responds to conventional medical intervention;
- Grade 3 nausea or vomiting that lasts $<$ 48 hours, and resolves to \leq Grade 1 either spontaneously or with conventional medical intervention;
- Grade 3 infusion reaction that resolves within 6 hours to \leq Grade 1;
- Alopecia;
- Grade 3 endocrinopathy that is adequately controlled by hormone replacement;
- Grade 3 tumor flare.
- Any Grade 4 or 5 Adverse Event (AE);
- Any Grade 2 drug-related uveitis or eye pain or blurred vision that does not respond to topical therapy and does not improve to Grade 1 severity within 2 weeks OR requires systemic treatment;
- Any treatment-related Grade 2 or greater toxicity that persists and results in an inability to administer C2D1.

For events that are not included in the above definitions, the SMC may declare any additional specific toxicity to be a DLT.

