6.6. Definition of Maximum Tolerated Dose and Recommended Phase 2 Dose

The MTD is defined as the JTX-2011 dose level that yields the largest estimated toxicity rate below 33%.

The RP2D, as well as administration time (currently a one-hour IV infusion each for JTX-2011 and nivolumab, 1.5-hour infusion for ipilimumab, and 30-minute infusion for pembrolizumab) and schedule will be determined in discussion among the Sponsor and Investigators. Observations related to safety, PK, pharmacodynamics, and IV infusion tolerability will be included in the rationale supporting the RP2D and schedule.

Observations related to safety, PK, pharmacodynamics, and IV infusion tolerability will be included in the rationale supporting the RP2D and schedule.

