7.2.2. Cycle 1 Day 2 (All Parts)

The following evaluations and procedures will be performed during this visit:

- Vital signs;
- Blood sample for PK, Cytokines, Immunophenotyping, Target Engagement;
- Record concomitant medications;
- Adverse events assessment.

7.2.3. Cycle 1 Day 4 (Part A, B, E, and G Sentinel Subjects Only)

- Targeted Physical Exam (as per institutional guidelines);
- Vital signs;
- Record concomitant medications;
- Adverse events assessment.

7.2.4. Cycle 1 Day 8 (Parts A, B, E, and G only, including AP1, AP2, BP1, BP2)

The following evaluations and procedures will be performed during this visit:

- Vital signs;
- Targeted Physical Exam (as per institutional guidelines)

- Laboratory Assessments: Chemistry, Hematology, Coagulation;
- Blood samples for PK, Immunophenotyping, and Target Engagement;
- Record concomitant medications;
- Adverse events assessment.

7.2.5. Cycle 1 Day 15 (Parts A and B [inc. AP1, AP2, BP1, BP2], E, and G only)

The following evaluations and procedures will be performed during this visit:

- Vital signs;
- Laboratory Assessments: Chemistry, Hematology, Coagulation;
- Blood samples for PK and Target Engagement;
- Record concomitant medications;
- Adverse events assessment.

7.2.6. Cycle 1 Day 22 (All cohorts in Parts E and F, q6w cohorts only in Parts C and H)

The following evaluations and procedures will be performed during this visit:

- Targeted Physical Exam.
- Laboratory Assessments: Chemistry, Hematology, Coagulation.
- Blood samples for PK/ADA/NAb, Cytokines, Immunophenotyping, Target Engagement.
- Record concomitant medications.
- Adverse events assessment.
- Part C (q6w) only:
 - Vital signs.
- Parts E and F only:
 - Weight.
 - Vital signs pre-and post-infusion.
 - Ipilimumab administration followed by observation for at least 1 hour.
- Part H only:
 - Weight.
 - Vital signs pre-and post-infusion.
 - Pembrolizumab administration followed by observation for at least 1 hour.

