8.14.6. Clinical Laboratory Evaluations

A clinical laboratory AE is any laboratory value that is considered clinically significant by the Investigator and has caused a medical intervention or accompanied by clinical symptoms. Laboratory abnormalities that have not required medical intervention should not be recorded as AEs and will be captured and reported in the Laboratory section of the clinical study report. If a medical intervention occurs, it should be recorded as a treatment with the abnormal laboratory finding as the AE.

The Investigator should decide, based upon the AE criteria and the clinical condition of the patient, whether a change in a laboratory parameter is clinically significant and therefore represents an AE.

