11.5. Modification of Protocol

All amendments to the protocol must be documented in writing, reviewed, and approved by the Investigator and Jounce, and submitted to the IRB for approval prior to initiation, except in cases where required for patient safety. If the protocol amendment substantially alters the study design or potential risk to the patient, new written informed consent for continued participation in the study must be obtained from each patient.

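### The DLT definition contradicts itself on Grade 4 events: a treated, short-lived, uncomplicated Grade 4 electrolyte event is exempted by one item and made a DLT by another

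*Protocol*

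**What the plan says.** Protocol 6.3, repeated in the Synopsis under Definition of DLT, gives a list of toxicities. Meeting any one item makes an event a DLT, provided it is at least possibly drug-related and falls in the first cycle. Two items in the non-hematological part matter here.

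- The item for toxicity of Grade 3 or worse carries ten exceptions. Seven stop at Grade 3, one (alopecia) has no grade, and two reach Grade 4. The first of those two is Grade 3 or 4 "elevation in serum amylase and/or lipase that are not associated with clinical or radiographic evidence of pancreatitis". The second is an electrolyte abnormality of Grade 3 or higher that lasts under 72 hours, "is not clinically complicated, and resolves spontaneously or responds to conventional medical intervention".
- A separate item at the same list level reads "Any Grade 4 or 5 Adverse Event (AE". It has no exception and does not refer back to the others.

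The section then says that, for events outside the listed definitions, "the SMC may declare any additional specific toxicity to be a DLT".

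Protocol 8.14.6 treats a laboratory value as an AE when the investigator finds it clinically significant and it "has caused a medical intervention or accompanied by clinical symptoms". Abnormalities that needed no medical intervention are kept out of AE recording. Protocol 8.8 is looser and asks only for clinical significance in the investigator's judgement.

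DLT counts drive the 3+3 rule in Protocol 6.2 and the definition in 6.6: "The MTD is defined as the JTX-2011 dose level that yields the largest estimated toxicity rate below 33" per cent. SAP 6.1.1 uses DLTs to define the DLT Evaluable Set, and SAP 9.9.1 lists and tabulates them. Neither section restates the definition.

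**The concern.** The protocol deliberately extends two exemptions to Grade 4 and then, further down the same list, makes every Grade 4 AE a DLT. Two careful readers could score the same event differently, each with text to rely on.

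The electrolyte exemption makes this more than a theoretical overlap. It expressly covers events that respond to treatment, and treatment is what turns a clinically significant laboratory value into an AE under 8.14.6. The feature that keeps the event inside the exemption also brings it under the Grade 4 or 5 item.

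Determining the MTD is a primary objective in Parts A, B, E and G, and with three to six subjects per dose level one event can change the decision. Classification also affects evaluability. A subject who leaves before the Cycle 2 Day 1 assessments is replaced unless a DLT occurred (Protocol 6.8.2).

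**Working it through.** The plan states no figure to reproduce. The check applies the two items to each exempted event, then carries one event through the 3+3 counts.

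**Step 1: apply both items.** All rows assume at least possible relatedness and onset in Cycle 1. The last two columns give the result of a literal any-item reading and of a reading in which the exemption prevails.

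| Event | Recorded as AE? | Grade 3-or-worse item | Grade 4 or 5 item | Literal | Exemption prevails |
|---|---|---|---|---|---|
| Grade 3 electrolyte, under 72 h, uncomplicated | either | exempt | not met | no DLT | no DLT |
| Grade 4 electrolyte, under 72 h, uncomplicated | no | exempt | not met | no DLT | no DLT |
| Grade 4 electrolyte, under 72 h, uncomplicated | yes | exempt | met | **DLT** | **no DLT** |
| Grade 3 amylase/lipase, no pancreatitis | either | exempt | not met | no DLT | no DLT |
| Grade 4 amylase/lipase, no pancreatitis | no | exempt | not met | no DLT | no DLT |
| Grade 4 amylase/lipase, no pancreatitis | yes | exempt | met | **DLT** | **no DLT** |

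The readings differ only for Grade 4 events recorded as AEs.

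**Step 2: see which of those rows is realistic.** Protocol Table 6 includes sodium, potassium, calcium, magnesium and phosphorus, so a Grade 4 electrolyte value can come from scheduled chemistry. If it is clinically significant and treated, it is an AE under 8.14.6 and remains within the exemption. That is the clear case. Amylase and lipase are not in Table 6, so a Grade 4 value would have to come from off-schedule testing and then be recorded as an AE.

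**Step 3: look for a rule of precedence.**

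- The SMC sentence in 6.3 only adds DLTs for events the list does not cover. This event is covered, twice.
- Protocol 6.7.3.1 adds DLTs for a first infusion stopped early and for AEs that warrant a Cycle 1 dose reduction. It does not rank the items in 6.3.
- Protocol 11.7 lets sites ask the medical monitor for clarification and allows study-wide memos. That is a route to an answer, not an answer.
- SAP 9.9.1 tabulates whatever was considered a DLT and gives no rule for this case.

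**Step 4: effect of one event on a cohort.**

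| Without the event | With the event | Consequence under 6.2 and 6.6 |
|---|---|---|
| 0/3 = 0% | 1/3 = 33.3% | escalate becomes expand to six |
| 1/6 = 16.7% | 2/6 = 33.3% | below 33% becomes not below 33%; MTD exceeded |

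This is what any single DLT does in a 3+3 design. It shows what a disputed event is worth, not how often one arises. The documents give no event rate from which a frequency could be worked out.

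**The case against.** The strongest reply is that the sensible reading is clear enough. A specific exemption with stated conditions normally prevails over a general catch-all, and nobody would write Grade 4 into two exemptions intending it to have no effect. One might answer that the Grade 4 or 5 item must do something, and that among non-hematologic events the only ones it adds are those exempted. That answer is weak, because the list already contains redundancy. Grade 4 AST or ALT of any duration has its own item, although the Grade 3-or-worse item already catches it and no exception reaches it. The Grade 4 or 5 item may be no more than a backstop. This reply stands as far as it goes: specific-over-general is reasonable. So is the conservative reading, and the text chooses neither.

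The second reply is that 8.14.6 removes much of the overlap. Untreated Grade 4 amylase/lipase values, and electrolyte values that resolve without treatment, are kept out of AE recording, so both items can operate. This also stands. A reader might infer that the Grade 4 or 5 item cancels both exemptions outright, and the documents do not support that. The clear conflict is the treated electrolyte event, with some uncertainty at the edge because 8.8 uses a looser test for an AE.

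Third, the medical monitor and the SMC could settle any actual case. SMC consensus is required to escalate (Protocol 6.2.2), and 11.7 provides for clarification. That limits the harm, but the written definition still gives two answers.

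Finally, little is left to act on. SAP section 4 reports all Phase 1 parts complete, and the DLT tables are descriptive. This limits the weight of the point and the scope of the fix.

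**Conclusion.** The point holds in narrow form. Protocol 6.3 and the Synopsis give two answers for a drug-related Cycle 1 Grade 4 electrolyte event that was treated and resolved within 72 hours without complication. The same conflict reaches Grade 4 amylase/lipase elevation without pancreatitis only when it was tested off-schedule and recorded as an AE. Nothing in either document ranks the two items.

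One such event is worth one DLT: 0/3 to 1/3, or 1/6 to 2/6. In the second case it carries the cohort across the MTD cut-off.

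A reader might infer that a DLT was miscounted, or that the MTD or the recommended Phase 2 dose is wrong. The documents do not support that. They record no such event, and SAP 3.2.4.1 says selection of the recommended dose was based on ICOS target engagement. What remains exposed is the reported DLT table, any MTD statement based on it, and any further escalation under this text.

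Confidence is high on the textual conflict. It does not extend to any consequence in this trial, which depends on whether such an event occurred.

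**What to change.** **For any further escalation.** Reword the item in Protocol 6.3 and the Synopsis to: *Any Grade 4 or 5 AE, except the amylase/lipase and electrolyte abnormalities exempted above.* If the sponsor prefers the conservative rule, limiting those two exemptions to Grade 3 also removes the conflict. Either is one clause in two places, but it changes a decision rule. It is therefore an amendment under Protocol 11.5, to be approved in writing and "submitted to the IRB for approval prior to initiation". Until then, sites can seek clarification from the medical monitor under 11.7. If no more escalation is run, the rewording is not needed.

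**For the CSR.** Keep DLTs as designated during the trial and do not re-score them, which is consistent with SAP 9.9.1. Check related Cycle 1 Grade 4 electrolyte and amylase/lipase AEs in Parts A, B, E and G. Footnote in the DLT table any event whose status differs between the two readings, with its effect on the cohort's count. If there is none, the question closes.

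**Cost.** One listing check across four parts and possibly a footnote. No new data are needed.

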6.4. Rules for Suspension of Dose Escalation

The SMC will recommend termination of dose escalation if any of the DLT conditions (see Section 6.2.2) are met in ≥ 2 of up to 6 subjects in a cohort. The SMC may also recommend suspension of JTX-2011 dose escalation based upon other conditions as deemed medically appropriate.

6.5. Safety/PK/PD Expansion Cohorts (AP1, AP2, BP1, BP2)

At each of two or more dose levels, approximately eight additional subjects will be enrolled for additional safety and PK/PD data. These subjects will be required to have biopsies of their tumors at baseline and after completion of 2 cycles of JTX-2011 for pharmacodynamics assessments. These subjects may be enrolled before, during, and after enrollment has commenced in Part C or D.

First Safety/PK/PD Expansion Cohort: If safety data are acceptable, Part A Safety/PK/PD Expansion Cohort 1 (AP1) and Part B Safety/PK/PD Expansion Cohort 1 (BP1) will be initiated at the first dose level of that Part at which there is approximately 70% Target Engagement (TE) in 2/3 subjects on Day 8.

Second Safety/PK/PD Expansion Cohort: If safety data are acceptable, Part A Safety/PK/PD Expansion Cohort 2 (AP2) and Part B Safety/PK/PD Expansion Cohort 2 (BP2) will be initiated at the lowest dose level at which there is approximately 70% TE in 2/3 subjects on Day 21, the MTD, or the highest dose studied.

The SMC will review safety data as outlined in the dose escalation phase for aggregate AEs for 9 weeks (e.g. through Cycle 3). Once a RP2D is determined, subjects at lower doses who remain on study treatment and are tolerating it well may increase their dose to the RP2D. In addition, the SMC will be convened approximately every 3 months to review accumulating safety data and patient disposition by cohort through the duration of the study.

6.6. Definition of Maximum Tolerated Dose and Recommended Phase 2 Dose

The MTD is defined as the JTX-2011 dose level that yields the largest estimated toxicity rate below 33%.

The RP2D, as well as administration time (currently a one-hour IV infusion each for JTX-2011 and nivolumab, 1.5-hour infusion for ipilimumab, and 30-minute infusion for pembrolizumab) and schedule will be determined in discussion among the Sponsor and Investigators. Observations related to safety, PK, pharmacodynamics, and IV infusion tolerability will be included in the rationale supporting the RP2D and schedule.

Observations related to safety, PK, pharmacodynamics, and IV infusion tolerability will be included in the rationale supporting the RP2D and schedule.

6.7. Criteria for Dose Modifications

6.7.1. Delayed Cycles

A change in the start of a cycle of +3 days for social reasons (e.g., holidays) is permitted if unavoidable. Subjects who require frequent treatment delays should be discussed with the Medical Monitor.

Subjects requiring a delay of a scheduled cycle starting on or after Cycle 3 due to treatment-related toxicities that have not resolved are to be managed as follows:

- If the delay is ≤ 7 days, treatment should resume at the assigned dose level.
- If the delay is > 7 days but ≤ 14 days, treatment should resume at the next lower dose level.
- If the delay is more than 14 days, further course of treatment should be discussed with the Medical Monitor.

If a cycle delay of > 14 days not due to treatment-related toxicity occurs, the circumstances surrounding the delay will be discussed with the Medical Monitor prior to dosing the patient for the next cycle.

6.7.2. Dose Interruptions

For study drug interruptions that occur for non-drug-related complications, the subject will remain on study as long as the study drug is infused within 6-hours of the interruption. If the interruption is due to toxicity, please refer to Section 6.7.3 for dose modifications.

6.7.3. Dose Modifications

6.7.3.1. Dose Modifications for JTX-2011

During dose-escalation, dose modifications are not allowed during Cycle 1, unless the subject experiences an infusion related reaction during the first administration of JTX-2011 which prevents the patient from receiving the first dose in its entirety. If, during the first dose, a subject experiences an infusion reaction where the Investigator determines the infusion should be terminated prematurely as a safety precaution, the event should be treated as a DLT according to Protocol Section 6.3.

The Investigator should then consult the Jounce Medical Monitor to determine if the patient should be either discontinued from the study, or proceed with future modified infusions (e.g., slower rate, lower dose group). Any AE that is severe enough (at the discretion of the Investigator and with permission of the Sponsor/CRO Medical Monitor) to warrant a dose reduction during Cycle 1 will be considered a DLT.

Dose Modifications and Management of Toxicity for JTX-2011 is provided in Table 5.

Table 5: Dose Modifications and Toxicity Management for JTX-2011, Nivolumab, Ipilimumab and Pembrolizumab

Adverse Event	Severity	Dose Modification	Recommended Management ^a
Diarrhea or Colitis	Grade 2	
Withhold study drug(s) until symptoms resolved to Grade 0-1.
 
If occurring in combination with nivolumab, ipilimumab or pembrolizumab, when symptoms resolved to Grade 0-1, resume JTX-2011. If symptoms do not recur after 1 cycle of JTX-2011, resume combination.^e
 
Permanently discontinue ipilimumab if symptoms last 6 weeks or longer or inability to reduce corticosteroid dose to 7.5 mg prednisone or equivalent per day
	If symptoms persist > 5 days or recur: 0.5 to 1 mg/kg/day prednisone equivalents followed by steroid taper ^a
	Grade 3	
Withhold study drug(s) until symptoms resolved to Grade 0-1.
 
If occurring in combination with nivolumab or pembrolizumab, when symptoms resolved to Grade 0-1, resume JTX-2011. If symptoms do not recur after 1 cycle of JTX-2011, resume combination.
 
Permanently discontinue if in combination with ipilimumab
	1-2 mg/kg/day prednisone equivalents followed by steroid taper ^a
	Grade 4	Permanently discontinue	1-2 mg/kg/day prednisone equivalents followed by steroid taper ^a
Pneumonitis	Grade 2	
Withhold study drug(s) until resolved to Grade 0-1
 
If occurring in combination with nivolumab, ipilimumab or pembrolizumab, when symptoms resolved to Grade 0-1, resume JTX-2011. If symptoms do not recur after 1 cycle of JTX-2011, resume combination.^e
 
Permanently discontinue study drugs if recurrent grade 2 pneumonitis in combination with pembrolizumab
	1-2 mg/kg/day prednisone equivalents followed by steroid taper ^a
	Permanently discontinue ipilimumab if symptoms last 6 weeks or longer	1-2 mg/kg/day prednisone equivalents followed by steroid taper ^a	

	Grade 3 or 4	Permanently discontinue	1-2 mg/kg/day prednisone taper ^a
Hepatitis	Grade 2 AST/ALT (>3 to 5 x ULN) or bilirubin (1.5 to 3 x ULN) ^b	Withhold study drug(s) until resolved to Grade 0-1. If occurring in combination with nivolumab, ipilimumab or pembrolizumab, when symptoms resolved to Grade 0-1, resume JTX-2011. If symptoms do not recur after 1 cycle of JTX-2011, resume combination. ^c	0.5 to 1 mg/kg/day prednisone equivalents or investigator discretion ^a
	Grade 3 or 4 AST/ALT (>5 x ULN) or bilirubin (>3 x ULN) ^b	Permanently discontinue ipilimumab if symptoms last 6 weeks or longer Permanently discontinue	1-2 mg/kg/day prednisone equivalents or investigator discretion ^a
Hypophysitis	Grade 2 or 3	Withhold study drug(s) until resolved to Grade 0-1 If occurring in combination with nivolumab, ipilimumab or pembrolizumab, when symptoms resolved to Grade 0-1, resume JTX-2011. If symptoms do not recur after 1 cycle of JTX-2011, resume combination. ^c	1 mg/kg/day prednisone equivalents ^a
	Grade 4	If occurring in combination with ipilimumab, permanently discontinue study drugs if symptomatic endocrinopathy lasts 6 weeks or longer or if there's inability to reduce corticosteroid dose to 7.5 mg prednisone or equivalent per day Permanently discontinue if not manageable with medical treatment	1 mg/kg/day prednisone equivalents ^a
Adrenal insufficiency	Grade 2	Withhold study drug(s) until resolved to Grade 0-1 If occurring in combination with nivolumab, ipilimumab or pembrolizumab, when symptoms resolved to Grade 0-1, resume JTX-2011. If symptoms do not recur after 1 cycle of JTX-2011, resume combination. ^c	Observation

		Permanently discontinue study drugs if symptomatic endocrinopathy in combination with ipilimumab lasts 6 weeks or longer or if there's inability to reduce corticosteroid dose to 7.5 mg prednisone or equivalent per day	
	Grade 4 hyperglycemia	Permanently discontinue if not manageable with medical treatment. Permanently discontinue study drugs if symptomatic endocrinopathy in combination with ipilimumab lasts 6 weeks or longer or if there's inability to reduce corticosteroid dose to 7.5 mg prednisone or equivalent per day	Administer insulin
Nephritis and Renal Dysfunction	Grade 2: serum creatinine (>1.5 to $3 \times$ ULN)	Withhold study drug(s) until resolution to Grade 0-1 If occurring in combination with nivolumab, ipilimumab or pembrolizumab, when resolved to Grade 0-1, resume JTX-2011. If increase in serum creatinine does not recur after 1 cycle of JTX-2011, resume combination. ^c	0.5 to 1 mg/kg/day prednisone equivalents followed by steroid taper. If worsening or no improvement occurs, increase dose of corticosteroids to 1-2 mg/kg/day prednisone equivalents and permanently discontinue. ^a
	Grade 3: serum creatinine (>3 to $6 \times$ ULN)	If occurring with monotherapy or in combination with nivolumab, withhold study drug(s). When resolved to Grade 0-1, resume JTX-2011. If increase in serum creatinine does not recur after 1 cycle of JTX-2011, resume combination, if applicable. Permanently discontinue study drugs if occurring in combination with pembrolizumab or ipilimumab	1-2 mg/kg/day prednisone equivalents ^a
Rash	Grade 4: serum creatinine ($>6 \times$ ULN)	Permanently discontinue	1-2 mg/kg/day prednisone equivalents ^a
	Grade 2	Only if occurring in combination with ipilimumab, withhold study drugs. When symptoms resolve to Grade 0-1, resume JTX-2011. If symptoms do not recur after 1 cycle of JTX-2011, resume combination. ^c	0.5 to 1 mg/kg/day prednisone equivalents ^a

	Grade 3	
Withhold study drug(s) until resolution to Grade 0-1.
 
If occurring in combination with nivolumab or pembrolizumab, when symptoms resolved to Grade 0-1, resume JTX-2011. If symptoms do not recur after 1 cycle of JTX-2011, resume combination.
 
Permanently discontinue if in combination with ipilimumab
 
Permanently discontinue
	1-2 mg/kg/day prednisone equivalents ^a
	Grade 4	Permanently discontinue	1-2 mg/kg/day prednisone equivalents ^a
Neuropathy	Grade 2	
Withhold study drug(s) until resolved to Grade 0-1; if symptoms persist \geq 6 weeks, subject continuation discussed between PI and Medical Monitor
 
If occurring in combination with nivolumab, ipilimumab or pembrolizumab, when symptoms resolved to Grade 0-1, resume JTX-2011. If symptoms do not recur after 1 cycle of JTX-2011, resume combination.^c
 
If occurring in combination with ipilimumab, permanently discontinue study drugs for related reactions lasting 6 weeks or longer or inability to reduce corticosteroid dose to 7.5 mg prednisone or equivalent per day
	None
	Grade 3	
Withhold study drug(s) until resolved to Grade 0-1; if symptoms persist \geq 6 weeks subject continuation discussed between PI and Medical Monitor
 
If occurring in combination with nivolumab or pembrolizumab, when symptoms resolved to Grade 0-1, resume JTX-2011. If symptoms do not recur after 1 cycle of JTX-2011, resume combination.
 
Permanently discontinue study drugs if occurred in combination with ipilimumab
 
Permanently discontinue
	1-2 mg/kg/day prednisone equivalents ^a
	Grade 4	Permanently discontinue	1-2 mg/kg/day prednisone equivalents ^a

Encephalitis	New-onset moderate or severe neurologic signs or symptoms	Permanently discontinue	If etiologies other than immune-mediated adverse event are ruled out, permanently discontinue JTX-2011 and administer 1-2 mg/kg/day prednisone equivalents ^a
	Immune-mediated encephalitis	Permanently discontinue	1-2 mg/kg/day prednisone equivalents ^a
Ophthalmologic	Uveitis, iritis, or episcleritis	Permanently discontinue if not resolved to Grade 0-1 with local immunosuppressive therapy	Corticosteroid eye drops
	Other Grade 3 adverse reaction	Withhold study drug(s) until resolution to Grade 0-1. If occurring in combination with nivolumab or pembrolizumab, when symptoms resolved to Grade 0-1, resume JTX-2011. If symptoms do not recur after 1 cycle of JTX-2011, resume combination.	Consider 1-2 mg/kg/day prednisone equivalents ^a
Other	Recurrence of same Grade 3 adverse reaction	Permanently discontinue study drugs if occurring in combination with ipilimumab Subject continuation discussed between PI and Medical Monitor	1-2 mg/kg/day prednisone equivalents ^a
	Life threatening or Grade 4 adverse reaction	Permanently discontinue	1-2 mg/kg/day prednisone equivalents ^a
	Requirement for 10 mg prednisone per day or greater prednisone or equivalent for > 12 weeks	Permanently discontinue	
	Persistent Grade 2 or 3 adverse reaction lasting ≥ 12 weeks	Subject continuation discussed between PI and Medical Monitor	

Abbreviations: ALT=alanine aminotransferase; AST=aspartate aminotransferase; ULN=upper limit of normal.
Toxicity graded per National Cancer Institute Common Terminology Criteria for Adverse Events Version 4.03 (NCI CTCAE v4.03)

- a If steroids have been administered, taper steroids per institution guidelines
- b Subjects with liver metastasis who begin combination therapy with pembrolizumab with Grade 2 AST or ALT, if AST or ALT increases by greater than or equal to 50% relative to baseline and lasts for at least 1 week, discontinue study drugs
- c Patients must have partial resolution of symptoms (Grade 0-1) and must be receiving less than 7.5mg of prednisone or equivalent per day in order to resume treatment with ipilimumab

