6.7.3.2. Dose Modifications and Toxicity Management for JTX-2011 in Combination with Nivolumab

For dose modifications for nivolumab please follow the prescribing information (Opdivo® Full Prescribing Information {Bristol-Myers Squibb Company 2017a}). In the event of a toxicity that requires that study treatment be withheld until resolution to Grade 0 or 1, the first administration of study drug after resolution of toxicity should be JTX-2011 alone. Nivolumab may be added at the next dose, at the discretion of the investigator and the medical monitor, if the toxicity does not recur with JTX-2011 monotherapy.

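### Table 5 gives opposing rechallenge instructions when a Grade 2 creatinine rise worsens to Grade 3 on first-step steroids, for JTX-2011 alone or with nivolumab

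*Protocol*

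**What the plan says.** The renal part of Table 5 (Protocol 6.7.3.1) grades creatinine as Grade 2 above 1.5 and up to 3 x ULN, Grade 3 above 3 and up to 6 x ULN, and Grade 4 above 6 x ULN.

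- **Grade 2, Dose Modification:** "Withhold study drug(s) until resolution to Grade 0-1". JTX-2011 is then restarted, followed by the partner drug if creatinine stays down for one cycle. This applies to all three partners.
- **Grade 2, Recommended Management:** steroids start at 0.5 to 1 mg/kg/day and are then tapered. The cell continues: "If worsening or no improvement occurs, increase dose of corticosteroids to 1-2 mg/kg/day prednisone equivalents and permanently discontinue". It names no partner drug and no upper grade.
- **Grade 3, Dose Modification, monotherapy or nivolumab:** "If occurring with monotherapy or in combination with nivolumab, withhold study drug(s). When resolved to Grade 0-1, resume JTX-2011". The combination follows if creatinine does not rise again after one cycle.
- **Grade 3, Dose Modification, other partners:** "Permanently discontinue study drugs if occurring in combination with pembrolizumab or ipilimumab".
- **Grade 3, Recommended Management:** steroids at 1-2 mg/kg/day.
- **Grade 4:** permanent stop for every regimen.

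**The concern.** Table 5 is an operating safety rule that a site applies to a subject with an organ toxicity. One instruction bars further study drug once first-step steroids have failed. The other directs a restart of JTX-2011 once creatinine has recovered. A Grade 2 event that becomes Grade 3 on steroids satisfies both, and nothing limits the Grade 3 row to events first seen at Grade 3.

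Column placement makes the stop easy to miss. It stands under Recommended Management, while the resume instruction stands under Dose Modification. A site that reads the dosing column to make a dosing decision would find the restart and not the stop. At stake is whether a subject whose nephritis progressed through steroids is given the drug again, and whether two sites would treat the same subject alike.

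**Working it through.** No calculation is needed to establish the conflict. The check compares the rows for a subject who starts at Grade 2 and worsens on 0.5-1 mg/kg/day, then looks for a rule that settles the difference.

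**Rows side by side**

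| Peak creatinine | Regimen | Grade 2 management cell | Row for the grade reached | Result |
|---|---|---|---|---|
| Up to 3 x ULN (still Grade 2, e.g. 2.0 to 2.8) | All | Permanent stop | Same row | Stop |
| Above 3 to 6 x ULN (e.g. 2.0 to 4.0) | Pembrolizumab or ipilimumab | Permanent stop | Permanent stop | Stop |
| Above 3 to 6 x ULN (e.g. 2.0 to 4.0) | Monotherapy or nivolumab | Permanent stop | Withhold, resume at Grade 0-1 | **Conflict** |
| Above 6 x ULN (e.g. 2.0 to 6.5) | All | Permanent stop | Permanent stop | Stop |

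The table shows where the conflict sits. It does not measure risk, because its cells are not equally likely.

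**What differs between the two readings.** The steroid dose is the same: the Grade 2 clause raises it to 1-2 mg/kg/day, and the Grade 3 row gives 1-2 mg/kg/day. Study drug is held during the toxicity under both. Only the decision after recovery to Grade 0-1 differs.

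**Order by severity if the Grade 3 row governed.** On monotherapy or nivolumab, after first-step steroids fail, a peak of 2.8 x ULN would end treatment, 4.0 would allow a restart, and 6.5 would end treatment. An intermediate peak would be handled more leniently than a lower one.

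**Search for a tie-breaker**

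- The Table 5 footnotes contain no rule for a creatinine rise that worsens from Grade 2.
- The Other rows of Table 5 cover recurrence of the same Grade 3 reaction, steroid need beyond 12 weeks, and Grade 2 or 3 reactions lasting 12 weeks or more. None covers escalation of a single event.
- Section 6.7.1 covers toxicity delays of cycles from Cycle 3 on. A delay of more than 7 and up to 14 days resumes at a lower dose level; beyond that, "If the delay is more than 14 days, further course of treatment should be discussed with the Medical Monitor". It does not rank the rows.
- Section 6.7.3.2 says "Nivolumab may be added at the next dose, at the discretion of the investigator and the medical monitor". That governs adding nivolumab back, not the restart of JTX-2011.
- Section 6.8 asks that withdrawal from treatment be discussed with the Medical Monitor where possible. Sections 6.8.1 and 11.7 give routes for clarification. None states a precedence.

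**Could broken table extraction explain it?** Row labels near these cells are displaced; the Grade 4 creatinine line, for example, falls under the Rash label. The two disputed cells can still be placed by content. A step up from 0.5-1 to 1-2 mg/kg/day fits only Grade 2, because Grade 3 already starts at 1-2. A split by partner drug fits only Grade 3, because Grade 2 resumes for all partners and Grade 4 stops for all. The narrower statement that the Grade 2 stop is absent from the Dose Modification cell depends on cell boundaries and should be confirmed against the PDF.

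**The case against.** The strongest reply is that the rows can be read together. The Grade 2 cell sets out a sequence, and worsening from Grade 2 naturally includes reaching Grade 3. It is the only text in the renal rows written for steroid failure, whereas the Grade 3 row has no earlier steroid step and so suits an event managed from Grade 3 onward. On this view the specific clause governs and the subject stops. The inverted severity order is then a reason to reject the other reading, not a harm in itself. This largely stands: it is the natural interpretation and the safer one. It remains an inference, because no sentence says so and the Grade 3 row, followed literally, directs a restart.

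The second reply is that the Medical Monitor would normally be involved. Section 6.8 asks for discussion before a subject comes off treatment, and it also lets the investigator or sponsor withdraw a subject for safety at any time. Together with 6.8.1, 11.7 and, from Cycle 3, 6.7.1, this makes an unreviewed rechallenge less likely. That stands too. It lowers the practical risk without supplying the rule.

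A reader might infer more than the documents support. They do not suggest dosing through active renal toxicity, since both readings withhold. The conflict does not extend to pembrolizumab, ipilimumab or Grade 4 events, where the rows agree. Nor does it bear on response rate, sample size, power or error rates.

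**Conclusion.** Two stated dosing rules conflict for one defined path: JTX-2011 alone or with nivolumab, creatinine worsening from Grade 2 to above 3 and up to 6 x ULN on first-step steroids. The protocol does not state which prevails. This is a minor correction to a safety rule, confined to rechallenge after recovery. How often the path would occur cannot be estimated, because the documents give no renal event rate.

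The conclusion rests on two assumptions. The first is that the two cells belong to the Grade 2 and Grade 3 renal rows, which their content supports. The second is that the stop in the Grade 2 clause refers to study drug; the clause does not name what is discontinued, but it raises steroids in the same sentence, so study drug is the natural reading. The nivolumab label cited in 6.7.3.2 is not among the documents. As that section cites it only for nivolumab dosing, it would not settle JTX-2011 dosing.

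**What to change.** 1. In the Grade 3 renal row, state that resumption does not apply to a Grade 2 event that worsened on corticosteroids, for which study drug(s) are permanently discontinued. The clinical team should confirm that this safer reading is the intended one.
2. In the Grade 2 Dose Modification cell, repeat the stop condition and name study drug(s), after checking the cell boundaries in the PDF.

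The cost is one sentence in each cell, with no new data, visits or procedures. For subjects still on treatment, section 11.7 allows study-wide updates by administrative memo where appropriate, which could carry the clarification.
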